### 3.1.3. Primary Safety Endpoints for Substudy A and Substudy B

Primary safety endpoints include both reactogenicity data and AEs collected from the e-diary and AE CRF.

Based on feedback from the FDA on multiple vaccine programs, reactogenicity data will utilize both e-diary data (prompted local reactions and systemic events) and reactogenicity events reported in the AE CRF during the e-diary collection period. Since the AE CRF did not designate a specific page to collect reactogenicity data for an untransmitted e-diary, Pfizer has adopted a process of providing a listing of AEs reported within 7 days after vaccination to the clinical team to review and determine (“flag”) which PTs should be considered reactogenicity events before the database lock. AEs reported on the same day of vaccination but missing the AE start time are defaulted to AEs reported after vaccination.

Following these review steps, those AEs reported within 7 days after vaccination that match with those flagged PTs will be considered reactogenicity data. If the same reactogenicity events are reported on the same day from both the e-diary and the AE CRF, the highest grade from the 2 data sources will be used for that specific day for analysis.

It should be noted that the data collection in the AE CRF is different from that of the e-diary:

- For redness, swelling, and fever, the measured size of redness and swelling at the injection site and temperature are recorded in the e-diary, but not in the AE CRF. As the missing e-diary entries are monitored with ongoing review of the prompted reactions reported in the AE CRF, any measurement recorded in the query response will be taken into consideration for the primary analysis using the data handling memo for analysis purposes. For the 7 days, only the maximum grading from both sources will be used for the aggregated severity analysis.
- For pain at the injection site and all other systemic events, the severity grading algorithm for the e-diary data and the AE CRF may not be the same, though Pfizer will choose the highest-severity grade.

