### **3.1.3.3. Adverse Events and Serious Adverse Events**

Standard algorithms for handling missing AE dates and missing AE severity will be applied as described in the Pfizer vaccine data standard rules. Completely missing AE start dates will not be imputed.

The following derivations will be included for each participant:

1. Any AE reported through 1 month after the last vaccination – If the AE started on the same day of the first vaccination, and if the AE start time is before the vaccination time, this AE would not be counted. Otherwise, if the AE start time is missing or after the vaccination time, the AE is included. Any AE reported 1 month after the last vaccination will not be included in the analysis.
2. Any related AE reported through 1 month after the last vaccination – Similar to the above except only a related AE is included (but excluding related reactogenicity reported within 7 days after vaccination).
3. Any immediate AE (AE start time is within 30 minutes after vaccination) reported after each (and any, if applicable) vaccination – Only include AEs that started on the same day of the vaccination and with nonmissing AE start time that is within 30 minutes of the vaccination. If the immediate AE is a related reactogenicity event, this would not be included as an immediate AE.
4. Any severe or life-threatening AE reported through 1 month after the last vaccination.
5. Any AE leading to study withdrawal after vaccination.
6. Any NDCMC reported throughout the study.
7. Any SAE reported throughout the study (including reactogenicity reported in the AE CRF during the e-diary collection period).
8. Any AESI reported throughout the study.

Any AE reported before the first vaccination will not be included in the derivation.

Variables 1 through 5 listed above will be derived with 2 approaches: excluding any reactogenicity (but not excluding reactogenicity SAEs) reported in the AE CRF during the e-diary collection period, and with no exclusion at all.

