##### 6.1.4.1. Main Analysis

- Estimand strategy: Treatment policy ([Section 2.2.1.3.2](#), [Section 2.2.1.3.3](#), [Section 2.2.1.3.4](#), [Section 2.2.1.4.2](#), [Section 2.2.1.4.3](#), and [Section 2.2.1.4.4](#)).
- Intercurrent events and missing data: All data collected are included.
- Analysis set: Safety population ([Section 4](#)).
- Analysis timing: At primary analyses (when all primary endpoint data are available).
- Analysis methodology: 95% CIs of the proportion of participants reporting those events will use the Clopper-Pearson method ([Section 5.2.1](#)).
- Descriptive statistics, including the proportion (%), the numerator (n) and the denominator (N) used in the proportion calculation, and the 95% CI for percentage using the Clopper-Pearson method, will be presented for each vaccine group for each analysis interval ([Section 5.2.1](#)).
- Bar charts with the proportions of participants for each variable within the specified interval will be plotted for each group. The bars may be divided into relatedness categories to highlight the proportions of participants with related events.
- The main analysis would be based on AEs excluding the reactogenicity events that were reported in the AE CRF (except for SAEs) ([Section 3.1.3.3](#)).

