##### 6.1.4.2. Supplementary Analysis

To support the assessment of AEs, the endpoints below, as specified in [Section 3.1.3.3](#), will be summarized with the same analysis population using the same presentation as specified in the main analysis:

- Immediate AEs after each (and any, if applicable) vaccination
- Related AEs reported through 1 month after the last vaccination
- Severe or life-threatening AEs reported through 1 month after the last vaccination
- AEs leading to withdrawal from vaccination throughout the study

- NDCMCs reported from vaccination throughout the study
- AESIs reported from vaccination throughout the study

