#### **6.1.4.3. Sensitivity Analysis**

In addition, a sensitivity analysis will be conducted by using all AEs (including reactogenicity reported in the AE CRF during the e-diary collection period).

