## 6.6. Safety Summaries and Analyses

### 6.6.1. Adverse Events

For all of the AEs categorized in [Section 3.1.3.3](#), each individual AE will be categorized by MedDRA and descriptively summarized by vaccine group.

A 3-tier approach will be used to summarize AEs. Under this approach, AEs are classified into 1 of 3 tiers ([Section 3.5.2](#)). For both Tier 1 and Tier 2 events, 2-sided 95% CIs, for the difference between the active vaccine and placebo groups in the percentage of participants reporting the events based on the Miettinen and Nurminen method, will be provided. In addition, for Tier 1 events, the asymptotic p-values will also be presented for the difference between groups in the percentage of participants reporting the events, based on the same test statistic and under the assumption that the test statistic is asymptotically normally distributed. AE displays will be sorted in descending order of point estimates of risk difference within the SOC. For Substudy A, the analysis of Tier 1 events is planned for comparing the RSVpreF vaccination group and the placebo vaccination group. For Substudy B, the analysis of Tier 1 events will be compared with the background rate that had similar population characteristics, considering no placebo group was included in Substudy B.

It should be recognized that most studies are not designed to reliably demonstrate a causal relationship between the use of a pharmaceutical product and an AE or a group of AEs. Except for select events in unique situations, studies do not employ formal adjudication procedures for the purpose of event classification. As such, safety analysis is generally considered an exploratory analysis and its purpose is to generate hypotheses for further investigation. The 3-tier approach facilitates this exploratory analysis.

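### Does the reactogenicity exclusion hide reactions that led participants to withdraw from the study?

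*SAP*

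**What the plan says.** SAP 3.1.3.3 lists eight derived adverse event variables. The fifth is "Any AE leading to study withdrawal after vaccination". The closing sentence of that section covers it: "Variables 1 through 5 listed above will be derived with 2 approaches: excluding any reactogenicity (but not excluding reactogenicity SAEs". The sentence goes on to limit the exclusion to reactions entered in the AE CRF during the e-diary period, and names the second approach as one with no exclusion.

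SAP 3.1.3 defines what counts as reactogenicity from the CRF: "those AEs reported within 7 days after vaccination that match with those flagged PTs will be considered reactogenicity data".

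The reporting sections then read as follows.

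- SAP 6.1.4.1: "The main analysis would be based on AEs excluding the reactogenicity events that were reported in the AE CRF (except for SAEs".
- SAP 6.1.4.2 refers to 3.1.3.3 for its endpoints, which "will be summarized with the same analysis population using the same presentation as specified in the main analysis". The withdrawal item is worded "AEs leading to withdrawal from vaccination throughout the study".
- SAP 6.1.4.3: "a sensitivity analysis will be conducted by using all AEs (including reactogenicity reported in the AE CRF during the e-diary collection period".
- SAP 6.6.1 refers to the 3.1.3.3 categories and says "each individual AE will be categorized by MedDRA and descriptively summarized by vaccine group", without naming a version.

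**The concern.** The protocol takes care to capture these events. Section 8.3.4 sends any prompted reaction that causes withdrawal to the AE page of the CRF, whether or not the investigator thinks it clinically significant. Section 8.4.1 requires any adverse event behind a study discontinuation to be on the CRF. Being on the AE page within 7 days of vaccination, with a flagged preferred term, is what places a nonserious reaction in the excluded class.

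The usual defense of the exclusion is that the reaction is reported elsewhere. That holds for occurrence and severity. It does not hold for withdrawal: the reactogenicity outputs in SAP 3.1.3.1 and 6.1.3 cover presence, maximum severity, duration and onset day, and none shows that a reaction ended participation.

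If only the exclusion version were tabulated, a reader could see no adverse events leading to withdrawal in a table while the disposition summary showed someone leaving because of one. In a study whose primary objectives include safety, that would be an awkward discrepancy.

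**Working it through.** The plan states no figure to reproduce, so the check is mainly textual.

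**Step 1: what each version counts.** Let A be the number of participants with a withdrawal event that is serious or is not flagged reactogenicity. Let B be the number whose only withdrawal events are nonserious, flagged and within 7 days of vaccination.

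- Exclusion version of variable 5: A.
- No-exclusion version: A + B.
- Difference: (A + B) − A = B.

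SAP 3.1.3.3 plans both derivations, so both the complete count and B can be obtained without new data or a new endpoint.

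**Step 2: which version goes where.** Set side by side, 6.1.4.1 takes the exclusion, 6.1.4.2 follows the main analysis in population and presentation, and 6.1.4.3 uses all events. The natural reading is that the withdrawal summary appears with the exclusion and again without it. Only 6.1.4.2 read alone leaves the version open.

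**Step 3: other routes to the same information.** SAP 6.5.2 tabulates withdrawals by reason and group, and plans listings of participants who withdrew. Protocol 7.2 includes adverse events among the reasons. A participant in B is therefore visible even if only the exclusion version were tabulated.

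**Step 4: size.** The denominators are 675 split 2:1, giving 675 × 2/3 = 450 and 675 × 1/3 = 225, and 200 in Substudy B. The shift per affected participant is:

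- 1/450 = 0.22 percentage points;
- 1/225 = 0.44;
- 1/200 = 0.50.

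To illustrate a single such participant when A = 0, with Clopper-Pearson 95% intervals:

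| Group | No exclusion | With exclusion |
|---|---|---|
| RSVpreF, Substudy A | 1/450, 0.22% (0.01 to 1.23) | 0/450, 0% (0 to 0.82) |
| Placebo, Substudy A | 1/225, 0.44% (0.01 to 2.45) | 0/225, 0% (0 to 1.63) |
| Substudy B | 1/200, 0.50% (0.01 to 2.75) | 0/200, 0% (0 to 1.83) |

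The single event is assumed. The documents give no rate of withdrawal due to reactions, so B cannot be estimated.

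**Step 5: what exempting variable 5 would do.** Suppose the exclusion were lifted for variable 5 only, and one RSVpreF recipient's sole event was a nonserious reaction that led to withdrawal. The main table would then show 0/450 for any adverse event (variable 1, exclusion kept) and 1/450 for events leading to withdrawal (variable 5). A subset would exceed the set that contains it. Treating variables 1 to 5 alike avoids this.

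**The case for a change.** The case for a change has real points. The SAP already departs from the exclusion where an event matters for its consequence: serious reactions are kept. Withdrawal could be argued to deserve the same treatment. If 6.1.4.2 does follow the main analysis, the leading withdrawal table is the incomplete one. If its reference to presentation means layout only, no version is chosen. SAP 6.1.4.3 does not name the supplementary endpoints, so one could read it as covering the main adverse event summaries alone. The SAP does not say that the disposition table shows the event term, severity or relatedness. Withdrawal counts are likely to be low, so one omission can turn a nonzero row into zero.

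The ambiguity in 6.1.4.2 and 6.1.4.3 stands. It does not follow that the plan must change. A version prespecified in 3.1.3.3 has no purpose unless it is reported, and the all-event analysis in 6.1.4.3 is the obvious place. Differing counts in two tables built on different stated definitions call for a table note.

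The withdrawal wording also differs between 3.1.3.3 and 6.1.4.2. In single-dose Substudy A the difference has no practical effect. In two-dose Substudy B it could matter, because Protocol 7.1 separates stopping vaccination from leaving the study. However, 6.1.4.2 points to 3.1.3.3 for its definitions, and study withdrawal is the only withdrawal variable defined there, so this is a clerical slip.

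A related worry concerns participants with no e-diary data. Their flagged nonserious reactions enter neither the main reactogenicity analysis nor the main adverse event analysis. SAP 3.1.3 gives its reason for leaving these participants out of the reactogenicity analysis (an inflated denominator and bias), and the all-event analysis in 6.1.4.3 picks up their CRF entries. A footnote counting them would change no result.

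**Conclusion.** No change to the plan follows. The exclusion does reach variable 5, and one of its two versions does omit nonserious Day 1 to 7 reactions that caused withdrawal. The complete version is prespecified in the same sentence, the neighboring sections indicate where each version belongs, and disposition and listings show the withdrawals independently. Exempting variable 5 alone would produce no result not already planned and could make the main table internally inconsistent.

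The possible effect on the exclusion version is 0.22 to 0.50 percentage points per affected participant, depending on the group. The number affected is unknown and probably small, since the event must be nonserious, flagged, within 7 days and the cause of study withdrawal. The summary is descriptive, and the noninferiority conclusion does not use it.

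This rests on two assumptions: that the no-exclusion derivation of variable 5 is tabulated, as its prespecification implies, and that table titles or footnotes say which version is shown. Both are ordinary table-shell decisions that an analyst would make sensibly without an SAP amendment.

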### **3.2. Secondary Endpoint**

#### **3.2.1. Substudy A Secondary Immunogenicity Endpoint**

RSV A– and RSV B–neutralizing antibody titers will be determined before vaccination, and at the 1-month postvaccination visit for Substudy A. The details of the secondary immunogenicity endpoint for Substudy A can refer to the primary immunogenicity endpoint for Substudy B in [Section 3.1.2](#).

### **3.3. Other Endpoint**

#### **3.3.1. Substudy B Other Immunogenicity Endpoint**

RSV seroresponse after each vaccination dose will be defined for each participant for subgroup A and subgroup B respectively:

- If pre-Dose 1 results are  $\geq$  LLOQ, seroresponse is achieved if there is a  $\geq 4$ -fold rise from postdose results.
- If pre-Dose 1 results are below LLOQ, seroresponse is achieved if the postdose titer is  $\geq 4 \times$  LLOQ.

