2.2.1. Clinical Overview

Adult Program Studies

The older adult program includes 2 Phase 1/2 studies, 3 Phase 3 studies, and a Phase 2a human challenge study.³⁰ The pediatric program has recently initiated with the Phase 1 portion of a Phase 1/2/3 study (C3671016).

- In the Phase 1/2 C3671001 study (NCT03529773), 1233 healthy adults 18 through 49 and 50 through 85 years of age received the 3 dose levels of RSVpreF (60 μ g, 120 μ g, and 240 μ g), with or without Al(OH)₃, or placebo, administered with or without concomitant influenza vaccine. The results have shown that the vaccine was well tolerated and immunogenic in both age groups. RSVpreF elicited robust neutralizing responses against RSV A and RSV B 1 month after vaccination for both age groups across all vaccine dose levels and formulations; these responses remained high through the 12 months after vaccination. In 616 vaccinated participants in the 50 through 85 years age group, RSV NT50 GMFRs were high across all arms, ranging from 9 through 13 from before vaccination to 1 month after vaccination and from 3 through 4 from before vaccination to 12 months for RSV A and RSV B. RSVpreF was safe and well tolerated when administered alone or with SIIIV, with no major differences observed across all dose levels and formulations. Most reported local reactions or systemic events were mild or moderate in severity. The proportions of participants reporting AEs were generally similar across RSVpreF groups, and no SAEs were considered related to the study intervention.
- In the Phase 1/2 C3671002 study (NCT03572062) in 250 older adults 65 through 85 years of age, 3 dose levels of RSVpreF with Al(OH)₃, or CpG/Al(OH)₃ (60 μ g, 120 μ g, and 240 μ g), given as a single dose or on a schedule of 2 doses administered 2 months apart were studied. All RSVpreF doses and formulations elicited high RSV A and RSV B neutralizing antibody GMTs 1 month after vaccination (GMFRs ranging from 4.8 to 11.6 and 4.5 to 14.1, respectively). CpG-containing formulations did not further increase neutralizing GMTs compared to RSVpreF with or without

Al(OH)₃. GMTs in all groups declined, but remained higher than baseline (before vaccination) and placebo (SITV only) at 12 months after vaccination (GMFRs ranging from 2.1 to 3.5 and 2.2 to 4.3, respectively). No increase in GMTs was observed 1 month after Vaccination 2 (GMFR of 0.9). All doses and formulations were safe and well tolerated.

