## **3. ENDPOINTS AND BASELINE VARIABLES: DEFINITIONS AND CONVENTIONS**

### **3.1. Primary Endpoints**

#### **3.1.1. Substudy A Primary Immunogenicity Endpoint**

RSV A- and RSV B-neutralizing antibody titers will be determined on sera collected before vaccination and at the 1-month postvaccination visit. NT data collected from Substudy A will be concurrently tested with the sera collected from C3671013 immunogenicity subset RSVpreF recipients at both the prevaccination visit and the 1-month postvaccination visit.

Titers above the LLOQ are considered accurate and their quantitated values will be reported. Refer to [Section 5.3.2](#) for LLOQ details. Titers below the corresponding LLOQ, or denoted as BLQ, will be set to  $0.5 \times$  LLOQ for analysis. Missing assay results will not be imputed.

In addition, RSV seroresponse after vaccination will be defined for each participant for subgroup A and subgroup B respectively:

- If prevaccination results are  $\geq$  LLOQ, seroresponse is achieved if there is a  $\geq 4$ -fold rise from prevaccination results.
- If prevaccination results are below LLOQ, seroresponse is achieved if the postvaccination titer is  $\geq 4 \times$  LLOQ.

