### 3.1.2. Substudy B Primary Immunogenicity Endpoint

RSV A– and RSV B–neutralizing antibody titers will be determined before the first dose, before the second dose, and 1 month after the second dose for Substudy B.

Titers above the LLOQ are considered accurate and their quantitated values will be reported. Refer to [Section 5.3.2](#) for LLOQ details. Titers below the corresponding LLOQ, or denoted as BLQ, will be set to  $0.5 \times$  LLOQ for analysis. Missing assay results will not be imputed.

RSV A and RSV B NTs at each blood sampling time point are included in the assay result data, thus no derivation is needed. The following variables will be derived for each participant:

1. RSV A/B at each blood sampling time point: This will be derived as the geometric mean of RSV A and RSV B NTs measured at each blood sampling time point for each participant.
2. RSV A, RSV B, and RSV A/B NT fold rise: This will be derived from before vaccination to each applicable postvaccination visit. The numerator is the postvaccination value and the denominator is the prevaccination value.

When calculating a fold rise, if assay results are  $<$  LLOQ, the assay results will be converted to  $0.5 \times$  LLOQ, except when the prevaccination assay result is  $<$  LLOQ while the postvaccination result is  $\geq$  LLOQ, in which case the prevaccination value will be set to LLOQ.

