### **3.4. Baseline Variables**

#### **3.4.1. Baseline Definition**

Day 1 is defined as the day of the vaccination for Substudy A and as the day of the first dose for Substudy B. Measurements or samples collected prior to the vaccination on Day 1 are considered the baseline data for the assessments.

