## 5. GENERAL METHODOLOGY AND CONVENTIONS

### 5.1. Hypotheses and Decision Rules

For the primary immunogenicity objective of Substudy A, there are a total of 4 tests (2 for RSV A and 2 for RSV B). The primary immunogenicity objective will be evaluated by the following null hypothesis:

- $H_0: \ln(\mu_1) - \ln(\mu_2) \leq -\ln(1.5)$  or  $p_1 - p_2 \leq -10\%$  vs
- $H_a: \ln(\mu_1) - \ln(\mu_2) > -\ln(1.5)$  and  $p_1 - p_2 > -10\%$

where  $-\ln(1.5)$  corresponds to a 1.5-fold margin for noninferiority in GMR,  $\ln(\mu_1)$  is the mean of the natural logarithm-transformed serum NT at 1 month after vaccination from participants who received the same dose level of RSVpreF in this study (participants  $\geq 18$  to  $< 60$  years of age with high-risk chronic medical conditions), and  $\ln(\mu_2)$  is the mean of the natural logarithm-transformed serum NT from participants who received RSVpreF in the C3671013 study immunogenicity subset (participants  $\geq 60$  years of age);  $-10\%$  is a noninferiority margin for seroresponse rate,  $p_1$  is the seroresponse rate at 1 month after vaccination from participants  $\geq 18$  to  $< 60$  years of age who received RSVpreF and are with high-risk chronic medical conditions, and  $p_2$  is the seroresponse rate at 1 month after vaccination from participants who received RSVpreF in the C3671013 study immunogenicity subset (participants  $\geq 60$  years of age).

Seroresponse is defined as a postvaccination antibody titer  $\geq 4$  times the LLOQ for a baseline titer below the LLOQ (seronegative), or a  $\geq 4$ -fold rise from baseline to after vaccination if the baseline titer is above the LLOQ (seropositive).

Noninferiority will be declared if both the null hypothesis of GMR and the null hypothesis of difference in seroresponse rates are rejected for both RSV A and RSV B serum NTs, with a type I error (2-sided) of 5%.

No multiplicity adjustment will be applied for this study because all 4 statistical hypotheses (2 endpoints for 2 RSV subgroups) must be rejected to declare noninferiority. Each of the 4 statistical tests will use a 2-sided alpha level of 0.05.

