### **6.3. Other Endpoint**

#### **6.3.1. Substudy B Other Immunogenicity Endpoint**

The rate of RSV A NT seroresponse and the rate of RSV B NT seroresponse after each dose will be descriptively summarized for participants in Substudy B.

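### SAP 3.3.1 states the Substudy B seroresponse rule with the wrong reference sample: a 4-fold rise from the postdose titer instead of from the pre-Dose 1 titer

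*SAP*

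**What the plan says.** SAP 3.3.1 introduces the endpoint with "RSV seroresponse after each vaccination dose will be defined for each participant for subgroup A and subgroup B respectively". Two branches follow. If the pre-Dose 1 result is below the LLOQ, the participant responds when the postdose titer is at least 4 times the LLOQ. If the pre-Dose 1 result is at or above the LLOQ, the participant responds on a 4-fold or greater "fold rise from postdose results". SAP 6.3.1 adds only that the RSV A and RSV B rates "after each dose will be descriptively summarized for participants in Substudy B".

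The related rules in the SAP use the sample before vaccination as the reference:

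- SAP 3.1.1 (Substudy A seroresponse): "fold rise from prevaccination results".
- SAP 5.1 (Substudy A hypotheses): "fold rise from baseline to after vaccination if the baseline titer is above the LLOQ".
- SAP 3.1.2 (Substudy B fold rise): "The numerator is the postvaccination value and the denominator is the prevaccination value".
- SAP 3.4.1 (baseline, where Day 1 in Substudy B is the day of the first dose): "Measurements or samples collected prior to the vaccination on Day 1 are considered the baseline data for the assessments".

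The protocol has no Substudy B seroresponse endpoint. Its section 10.8.3 lists GMTs and GMFRs only.

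**The concern.** A rise from a sample takes that sample as its reference, so the upper branch in SAP 3.3.1 starts the rise at the postdose titer and names no end point. This is the only place where the Substudy B seroresponse rule is written out, so it is the text a programmer would work from. Substudy B gives two doses, and protocol 10.8.4.3 presents the second dose as something to be assessed. A reader could therefore take the phrase to mean an incremental response from post-Dose 1 to post-Dose 2.

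At stake are the Substudy B seroresponse rates. Protocol 10.8.9.1 allows Substudy B immunogenicity data to be compared descriptively with other studies, and 10.8.9.4.1 allows ongoing summaries for decision-making. A rate built on another reference sample would not be comparable with the Substudy A rate of the same name.

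**Working it through.** The documents give no seroresponse rate, power or statistical sample-size basis for Substudy B, so there is no planned figure to reproduce. The check is of the text, followed by an illustration of scale.

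**1. What the literal rule can compute.** SAP 3.1.2 gives three samples: T0 (before Dose 1), T1 (before Dose 2, which is 1 month after Dose 1) and T2 (1 month after Dose 2).

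| Rate reported | Rule in line with SAP 3.1.1, 3.1.2, 3.4.1 and 5.1 | Literal SAP 3.3.1 (rise from the postdose sample) |
|---|---|---|
| After Dose 1 | T1/T0 ≥ 4 | Reference T1; the only later sample is T2, which is not a Dose 1 response |
| After Dose 2 | T2/T0 ≥ 4 | Reference T2; there is no later sample |

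The only computable 4-fold rise from a postdose sample is T2/T1 ≥ 4.

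**2. One participant.** Take T0 = 1000, T1 = 9000, T2 = 8100.

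- T1/T0 = 9.0 and T2/T0 = 8.1: responder after both doses.
- T2/T1 = 8100/9000 = 0.9: non-responder.

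**3. Scale, as illustration only.** For a log-normal fold rise, P(fold ≥ 4) = 1 − Φ((ln 4 − ln GMFR)/SD). Inputs:

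- Dose 1 GMFR of 9 to 13, from adults aged 50 through 85 in a Phase 1/2 study (protocol 2.2.1).
- Second-dose GMFR of 0.9, from the Phase 1/2 study in adults aged 65 through 85 with doses 2 months apart (protocol 2.2.1: "No increase in GMTs was observed 1 month after Vaccination 2 (GMFR of 0.9"). It is used here as T2/T1.
- SDs of the ln fold rise are assumed, because the documents give none: 0.4 to 1.0 for T2/T1, and 0.8 to 1.2 for rises from T0.

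Between doses, ln 4 − ln 0.9 = 1.386 + 0.105 = 1.492:

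| Assumed SD | z = 1.492/SD | P(T2/T1 ≥ 4) |
|---|---|---|
| 0.4 | 3.73 | 0.01% |
| 0.6 | 2.49 | 0.65% |
| 0.8 | 1.86 | 3.1% |
| 1.0 | 1.49 | 6.8% |

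Measured from T0, over the assumed SDs:

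| GMFR from T0 | P(fold ≥ 4) |
|---|---|
| After Dose 1: 9 | 75.0% to 84.5% |
| After Dose 1: 13 | 83.7% to 93.0% |
| After Dose 2: 9 × 0.9 = 8.1 | 72.2% to 81.1% |
| After Dose 2: 13 × 0.9 = 11.7 | 81.4% to 91.0% |

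**4. A less extreme case.** Assume a weaker Dose 1 GMFR of 3 to 5 and a second dose that doubles titers (GMFR 2.0). The between-dose rule then gives 4% to 24%. The rule from T0 after Dose 2 (GMFR 6 to 10) gives 63% to 87%. The two readings still give very different rates.

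**The case against.** The strongest reply is that the intent is plain. The branch is itself conditioned on the pre-Dose 1 result. SAP 3.1.2, the Substudy B section, puts the prevaccination value in the denominator. SAP 3.4.1 fixes baseline before the first dose, and 3.1.1 and 5.1 define the same endpoint from baseline in Substudy A. The phrase may only have meant a rise seen in the postdose result. A rule that cannot be programmed literally would also be expected to raise a query before it produced a wrong rate. All of this stands, and it limits the finding to a misstated rule whose meaning can be recovered.

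It does not remove the need for correction. The sections that point to the intent either cover Substudy A or define fold rise and baseline in general. None of them states the Substudy B seroresponse rule.

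The consequence is also small. SAP 3.3 classes this as an other endpoint, it is summarized descriptively, and protocol 10.8.9.1 rules out hypothesis testing in Substudy B. Only participants at or above the LLOQ before Dose 1 are affected.

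A reader might infer more than the documents support:

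- *That nothing else in the plan points to the right reference.* SAP 3.1.2, 3.4.1 and 5.1 do.
- *That seroresponse is the only Substudy B measure that lines up with Substudy A.* GMTs of the same RSV A and RSV B titers line up too, and this wording does not touch them.
- *That the two branches of 3.3.1 measure different things.* Substudy A has the same two-branch structure. The mismatch arises only if the between-dose reading is adopted.

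**Conclusion.** The point holds as a wording error in a prespecified definition. SAP 3.3.1 reverses the reference sample. Read literally, it is either not computable after each dose or becomes a post-Dose 2 to post-Dose 1 rise that misclassifies participants.

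It is tempting to conclude that the analysis will report a wrong responder rate. The documents do not support that: the wrong rate needs a reading that contradicts SAP 3.1.2 and the branch's own condition. It is an avoidable risk, confined to the Substudy B seroresponse rates. The Substudy A primary analysis, the Substudy B GMTs and GMFRs, and the safety analyses are unaffected.

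The percentages show how far apart the two readings can be and do not predict Substudy B results. They rest on assumed SDs and on GMFRs from other populations. The 0.9 comes from older adults dosed 2 months apart, whereas Substudy B doses immunocompromised adults 1 month apart. Protocol 10.8.4.3 says no RSVpreF immunogenicity data exist for them. The three-titer example needs none of these assumptions.

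**What to change.** Replace the upper branch in SAP 3.3.1 with:

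> If the pre-Dose 1 result is ≥ LLOQ, seroresponse after a dose is achieved if the postdose titer is ≥ 4 times the pre-Dose 1 titer.

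State that this applies to both the post-Dose 1 and the post-Dose 2 samples. The branch for results below the LLOQ can stay as it is.

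The cost is one sentence in the SAP. It needs no new data, no change in sample size and no protocol amendment, because the protocol does not define this endpoint.
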